6.3.12 Tumour Tissue Collection and Correlative Studies Blood Sampling

6.3.12.1 Archival Tumour tissue samples

For patients where a screening biopsy is not feasible, archival tumour material must be provided. If archived biopsy (block or slides) are sent it must contain tumour tissue. If no block is available, 10 or more freshly prepared (generated within the last 6 months) unstained 5 micron sections should be provided. Archival tumour blocks will be returned to source at the end of the study or, upon request, earlier if required for the patient's clinical management. Cut sections will be retained by the study team. These are archived samples and as such participating patients will not need to attend extra visits or undergo extra procedures. All collected archival samples will be classed as pre-treatment samples and used as such in the immunological evaluation as described below.

6.3.13 Tumour Biopsies and Research Blood Samples

For patients without archived samples, tumour biopsies will be obtained during the screening period. If the patient consents optional research blood samples will be obtained at C1D1, C2D1, C5D1 and at the end of study visit (Table 3). Tumour and blood samples from this study may undergo proteomic, genomic and transcriptional analyses. Additional research may evaluate factors important for predicting responsiveness or resistance to pembrolizumab therapy and radiotherapy. Assays may include, but are not limited to:

- **Characterisation of TILs and tumour antigens**

Immunohistochemistry (IHC) will be used to assess the number and composition of immune infiltrates in order to define the immune cell subsets present within formalin-fixed, paraffin embedded (FFPE) tumour tissue before and after exposure to therapy. These IHC analyses will include, but not necessarily be limited to, the following: CD4, CD8, FOXP3, PD-1, PD-L1, and PD-L2.

- **ctDNA & CTCs**

Research blood samples will be analysed for ctDNA and CTCs. Analysis of CTCs will include, but not necessarily limited to the following, the diagnostic performance of PD-L1 testing will be assessed in CTC compared with IHC, correlation with response and disease progression.

6.3.14 Chain of Custody of Biological Samples

In all cases, patients will be consented for the collection and use of their biological samples and a full chain of custody will be maintained for all samples throughout their lifecycle. The Investigator is responsible for maintaining a record of full traceability of biological samples collected from patients while these are in storage at the site, either until shipment or disposal. Anyone with custody of the samples e.g. sub-contracted service provider will have to keep full traceability of samples from receipt to further shipment or disposal (as appropriate). RM-CTU will keep overall oversight of the entire lifecycle through internal procedures and monitoring of study site.

6.4 Total Blood Volume

The total volume of blood that will be drawn from each trial patient for the assessments described in the sections above is shown in Table 5.

Table 5: Volume of blood

	Sample volume (ml)	No. of samples	Total volume (ml)
Routine Haematology	6 ¹	11	66
Routine Chemistry	8 ¹	11	88
Routine Total:			154
Research Blood Samples OPTIONAL	60	4	240
Study Total:			394

¹Blood volumes may vary according to local practice

7 TREATMENTS

7.1 SBRT for pleural mesothelioma

7.1.1 Planning and Delivery

Radiotherapy planning and delivery should be carried out in accordance with the current RTT QA guidelines for stereotactic radiotherapy trials available on request from RMH-CTSU and included as Appendix 3 within the protocol. As only part of a MPM lesion may be treated the target coverage planning goals will be for the defined target volumes.

7.1.2 Toxicity Assessments

Dyspnoea score and toxicity grading with CTCAE v5.0 will be recorded and will include pneumonitis, lung fibrosis, oesophagitis, skin toxicity, myelitis and fatigue. All other AEs will be documented in addition.

7.2 Pembrolizumab

7.2.1 Investigational Product

The Investigational Medicinal Product (IMP) for this study is pembrolizumab. A potent and highly-selective humanized mAb of the IgG4/kappa isotype designed to directly block the interaction between PD-1 and its ligands, PD-L1 and PD-L2. Pembrolizumab potentiates existing immune responses only in the presence of antigen and does not non-specifically activate T-cells. Pembrolizumab will be manufactured by MSD according to Good Manufacturing Practice and will be provided in the formulation as described in Table 6. Additional information about the investigational product can be found in the Investigator's Brochure (IB).

Table 6: Product Description

Product Name & Potency	Formulation
Pembrolizumab 100 mg/ 4mL	Solution for Infusion

7.2.2 Product Preparation

Please refer to the RM Pharmacy Manual for preparation of the pembrolizumab for infusion.

7.2.3 Storage and Handling

7.2.3.1 Storage

Please refer to the RM Pharmacy Manual for stability information on drug stability and storage.

7.2.3.2 Handling

Please refer to the RM Pharmacy Manual for IMP handling instructions. Specific details on the preparation of the drug product can be found in the RM pharmacy manual. At each site the Principle Investigator/designee e.g. pharmacist at each participating site is responsible for ensuring that all trial Medication must be stored in a secure, limited-access location under the storage conditions specified on the label. Receipt and dispensing of trial medication must be recorded by an authorised person at the trial site. Trial medication may not be used for any purpose other than that stated in the protocol.

Sites should follow their SOPs for drug transport and delivery, with all possible effort to minimise agitation of the reconstituted drug product between the pharmacy and the clinic.

7.2.4 Packaging and Labelling Information

Pembrolizumab will be supplied by MSD as solution for injection. Pembrolizumab will be packaged, labelled and delivered to the participating sites free of charge by MSD. The IMP will be supplied specifically for the trial and should not be used for any other purpose than that stated in this protocol. The drug will be labelled in accordance to Good Manufacturing Practice Annex 13.

7.2.5 Returns and Reconciliation

The Principle Investigator/designees is responsible for keeping accurate accountability accurate records for pembrolizumab including the amount dispensed to and returned for each patient and the amount remaining on site at the conclusion of the trial. Upon completion or termination of the study, all unused and/or partially used trial medication will be destroyed at the site per institutional policy. It is the Principle Investigator's/designees responsibility to arrange for disposal of all empty containers, provided that procedures for proper disposal have been established according to applicable federal, state, local and institutional guidelines and procedures, and provided that appropriate records of disposal are kept.

7.2.6 Doses and Treatment Regimens

All patients will receive pembrolizumab administered as per standard procedures following manufacturer's instructions. Trial treatment should begin on the day of confirmation of eligibility or as close as possible to the date on which treatment is allocated/assigned.

Table 7: Pembrolizumab and SBRT for MPM schedules

Dose level	Lung SBRT	Drug	Dose	Dose Frequency	Route of Administration
Part A	30 Gy in 3#	Pembrolizumab	200 mg	3 weekly	IV infusion
Part B	30 Gy in 3#	Pembrolizumab	200 mg	3 weekly	IV infusion

7.2.7 Timing of Dose Administration

During the induction and maintenance phase, the pembrolizumab should be administered on Day 1 of each cycle after all procedures/assessments have been completed as detailed on the schedule of study assessments (Table 3). The pembrolizumab administration may be administered up to 3 days before or after the scheduled Day 1 during the induction and maintenance phase due to administrative reasons. During the induction and maintenance phase of the trial, the pembrolizumab will be administered on a 3 weekly cycle (Table 3).

Maintenance pembrolizumab will continue until disease progression, withdrawal of consent, or unacceptable toxicity. Patients obtaining complete response or having completed 35 cycles of pembrolizumab have the option of discontinuing treatment, with a view to restarting treatment on disease progression. Retreatment should be discussed with the Chief Investigator and the sponsor. Study related assessment and procedures should be as for the beyond DLT Pembrolizumab Maintenance phase (see Table 3). Patients do not need to re-sign the consent form for restarting treatment, provided their consent is on the most up-to-date version of the Patient Information Sheet Consent Form.

All trial treatments will be administered on an outpatient basis. Pembrolizumab will be administered as a 30 minute IV infusion (treatment cycle intervals or infusion length may be increased due to toxicity as described in Section 6.2.9.2). Sites should make every effort to target infusion timing to be as close to 30 minutes as possible. However, given the variability of infusion pumps from site to site, a window of -5 minutes and +10 minutes is permitted (i.e., infusion time is 30 minutes: -5 min/+10 min). The RM Pharmacy Manual contains specific instructions for pembrolizumab, reconstitution, preparation of the infusion fluid, and administration. In addition, infusion length may be increased due to toxicity as described in Section 6 and Table 9.

The RM pharmacy manual contains specific instructions for pembrolizumab reconstitution, preparation of the infusion, and administration.

7.2.8 Blinding/Masking

This is an open-label trial; therefore, the Sponsor, investigator and patient will know the treatment administered.

7.2.9 Dose Selection/Modification

7.2.9.1 Dose Selection

Pembrolizumab is being given using standard 200 mg flat dosing every three weeks. The Pembrolizumab dosing interval may be increased due to toxicity as described in Section 3.1.1. Details on the preparation and administration of pembrolizumab are provided in the RM Pharmacy Manual. These guidelines contain specific instructions for pembrolizumab reconstitution, preparation of the infusion fluid and administration.

7.2.9.2 Dose Modification

Pembrolizumab will be withheld for drug-related Grade 4 haematological toxicities, and non-haematological toxicity \geq Grade 3 including laboratory abnormalities, and severe or life-threatening AEs as per Table 8 below.

In case toxicity does not resolve to Grade 0-1 within 12 weeks after last infusion, trial treatment should be discontinued after consultation with the Sponsor. With Investigator and Sponsor agreement, patients with a laboratory AE still at Grade 2 after 12 weeks may continue treatment in the trial only if asymptomatic and controlled. For information on the management of AEs, see Section 6 and Table 8.

Patients who experience a recurrence of the same severe or life-threatening event at the same grade or greater with re-challenge of pembrolizumab should be discontinued from trial treatment.

Events of Clinical interest (ECI) can be potential irAEs and dose modifications for these toxicities should they occur can be found in Appendix 5.

Dosing interruptions are permitted in the case of medical / surgical events or logistical reasons not related to study therapy (e.g., elective surgery, unrelated medical events, patient vacation, and/or holidays). Subjects should be placed back on study therapy within 3 weeks of the scheduled interruption, unless otherwise discussed with the Sponsor. The reason for interruption should be documented in the patient's study record.

Table 8: Dose modification guidelines for drug-related adverse events.

Toxicity	Hold Treatment for Grade	Timing for Restarting Treatment	Treatment Discontinuation
Diarrhoea/Colitis	2-3	Toxicity resolves to Grade 0-1/baseline.	Toxicity does not resolve within 12 weeks of last dose or inability to reduce corticosteroid to 10 mg or less of prednisone or equivalent per day within 12 weeks.
	4	Permanently discontinue	Permanently discontinue
AST, ALT, or Increased Bilirubin	2	Toxicity resolves to Grade 0-1	Toxicity does not resolve within 12 weeks of last dose.
	3-4	Permanently discontinue (see exception below) ¹	Permanently discontinue
Type 1 diabetes mellitus (if new onset) or Hyperglycemia	T1DM or 3-4	Hold pembrolizumab for new onset Type 1 diabetes mellitus or Grade 3-4 hyperglycemia associated with evidence of beta cell failure.	Resume pembrolizumab when patients are clinically and metabolically stable.
Hypophysitis	2-4	Toxicity resolves to Grade 0-1. Therapy with pembrolizumab can be continued while endocrine replacement therapy is instituted	Toxicity does not resolve within 12 weeks of last dose or inability to reduce corticosteroid to 10 mg or less of prednisone or equivalent per day within 12 weeks.
Hyperthyroidism	3	Toxicity resolves to Grade 0-1	Toxicity does not resolve within 12 weeks of last dose or inability to reduce corticosteroid to 10 mg or less of prednisone or equivalent per day within 12 weeks.
	4	Permanently discontinue	Permanently discontinue
Hypothyroidism		Therapy with pembrolizumab can be continued while thyroid replacement therapy is instituted	Therapy with pembrolizumab can be continued while thyroid replacement therapy is instituted.
Infusion Reaction	3-4	Permanently discontinue	Permanently discontinue
Pneumonitis	2	Toxicity resolves to Grade 0-1. If recurrent grade 2 pneumonitis occurs pembrolizumab should be permanently discontinued.	Toxicity does not resolve within 12 weeks of last dose or inability to reduce corticosteroid to 10 mg or less of prednisone or equivalent per day within 12 weeks.
	3-4	Permanently discontinue	Permanently discontinue
Renal Failure or Nephritis	2	Toxicity resolves to Grade 0-1	Toxicity does not resolve within 12 weeks of last dose or inability to reduce corticosteroid to 10 mg or less of prednisone or equivalent per day within 12 weeks.
	3-4	Permanently discontinue	Permanently discontinue
Hepatitis	1	Continue treatment	
	2 - 4	Withhold treatment	Treat with steroids (prednisone 1 – 2 mg/kg or equivalent). Restart treatment when all liver function tests are down to grade 1 and steroid dose is down to 10 mg or less of prednisone or equivalent. Based on severity and symptoms you may wish to discontinue treatment.
Myocarditis	1 – 2	Withhold treatment	Treat with steroids (prednisone 1 – 2 mg/kg or equivalent). Restart treatment when symptoms are down to grade 1 and steroid dose is down to 10 mg or less of prednisone or equivalent.
	3-4	Permanently discontinue	Permanently discontinue
Skin reactions	1 – 2	Continue treatment	Manage with topical corticosteroids and oral anti-purpuras
	3	Withhold treatment	Treat with steroids (prednisone 1 – 2 mg/kg or equivalent). Restart treatment when rash is down to grade 1 and steroid dose is down to 10 mg or less of prednisone or equivalent.

Toxicity	Hold Treatment for Grade	Timing for Restarting Treatment	Treatment Discontinuation
	4	Permanently discontinue	Permanently discontinue
Confirmed Stevens-Johnson Syndrome or Toxic-epidermal Necrolysis	-	Permanently discontinue	Permanently discontinue
All Other Drug-Related Toxicity ²	3 or Severe	Toxicity resolves to Grade 0-1	Toxicity does not resolve within 12 weeks of last dose or inability to reduce corticosteroid to 10 mg or less of prednisone or equivalent per day within 12 weeks.
	4	Permanently discontinue	Permanently discontinue

Note: Permanently discontinue for any severe or Grade 3 drug-related AE that recurs or any life-threatening event.

¹ For patients with liver metastasis who begin treatment with Grade 2 AST or ALT, if AST or ALT increases by greater than or equal to 50% relative to baseline and lasts for at least 1 week then patients should be discontinued.

² Patients with intolerable or persistent Grade 2 drug-related AE may hold study medication at physician discretion. Permanently discontinue study drug for persistent Grade 2 adverse reactions for which treatment with study drug has been held, that do not recover to Grade 0-1 within 12 weeks of the last dose.

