irAE	Withhold/Discontinue Pembrolizumab?	Supportive Care
Grade 1	No action	Provide symptomatic treatment
Grade 2	May withhold pembrolizumab. For recurrent grade 2 pneumonitis, pembrolizumab should be discontinued permanently.	Consider systemic corticosteroids in addition to appropriate symptomatic treatment. Steroid taper should be considered once symptoms improve to Grade 1 or less and tapered over at least 4 weeks. Based on limited data from clinical studies in subjects whose immune-related adverse reactions could not be controlled with corticosteroid use, administration of other systemic immunosuppressants can be considered.
Grade 3 and Grade 4	Withhold pembrolizumab Discontinue if unable to reduce corticosteroid dose to < 10 mg per day prednisone equivalent within 12 weeks of toxicity	Systemic corticosteroids are indicated in addition to appropriate symptomatic treatment. May utilize 1 to 2 mg/kg prednisone or equivalent per day. Steroid taper should be considered once symptoms improve to Grade 1 or less and tapered over at least 4 weeks. Based on limited data from clinical studies in subjects whose immune-related adverse reactions could not be controlled with corticosteroid use, administration of other systemic immunosuppressants can be considered.
Please Note: If an irAE does not resolve or improve to \leq Grade 1 within 12 weeks after last administration of pembrolizumab, study therapy discontinuation should be considered after discussion with a Merck Clinical Director via the RM-CTU trial manager.		

Details for managing specific irAEs are summarised below:

Immune-mediated pneumonitis

Monitor subjects for signs and symptoms of pneumonitis. If pneumonitis is suspected, evaluate with radiographic imaging and exclude other causes. Administer corticosteroids for Grade 2 or greater events (initial dose of 1-2 mg/kg/day prednisone or equivalent followed by a taper), withhold pembrolizumab for moderate (Grade 2) pneumonitis, and permanently discontinue pembrolizumab for recurrent moderate (Grade 2), severe (Grade 3) or life-threatening (Grade 4) pneumonitis.

Immune-mediated colitis

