	Grade 2	
 Withhold pembrolizumab, may restart if Grade 1 or resolved within 12 weeks Consider Haematology consultation 	
 Prednisone 1-2mg/kg daily Permanently discontinue pembrolizumab if dose cannot be reduced to prednisone 10mg or less or equivalent per day within 12 weeks.
	Grade 3	
 Withhold pembrolizumab, may restart if Grade 1 or resolved within 12 weeks Recommend Haematology consultation 	
 IV methylprednisolone 125mg or Prednisone 1-2mg/kg p.o. (or equivalent) as appropriate. Permanently discontinue pembrolizumab if corticosteroid dose cannot be reduced to prednisone 10mg or less or equivalent per day within 12 weeks.
	Grade 4	
 Discontinue pembrolizumab Recommend Haematology consultation 	
 IV methylprednisolone 125mg or Prednisone 1-2mg/kg p.o. (or equivalent) as appropriate.
Hepatic – Drug induced Liver Injury (DILI). Please refer to Section 6 and 7 for definitions of (DILI)	Grade 1 (Asymptomatic)	
 No action 	
 Intervention not indicated
	Grade 2	
 Report liver toxicity ECIs within 24 hours, as detailed in Section 7.5.2. Withhold Pembrolizumab if AST or ALT >3.0 to 5.0 X ULN and/or total bilirubin is >1.5 to 3.0 X ULN Monitoring Liver function until values return to baseline 	
 0.5-1mg/kg/day methylprednisolone 125mg or oral equivalent. LFT grade 1 or less initiate steroid taper for no less than 4 weeks. Consider prophylactic antibiotics and resume pembrolizumab. Permanently discontinue pembrolizumab if dose cannot be reduced to prednisone 10mg or less or equivalent per day within 12 weeks.

			
 Permanently discontinue pembrolizumab for patients with liver mets who begin treatment with grade 2 elevation of AST or ALT and AST or ALT increase $\geq 50\%$ relative to baseline and lasts ≥ 1 week.

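### Section 7.2.9.2 and its own Table 8 disagree on when haematological toxicity holds or stops pembrolizumab, and on a laboratory AE still at grade 2 after 12 weeks

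*Protocol*

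**What the plan says.** Section 7.2.9.2 opens with running text. On haematological toxicity it says: "Pembrolizumab will be withheld for drug-related Grade 4 haematological toxicities". The same sentence adds non-haematological toxicity from grade 3, and severe or life-threatening events by reference to Table 8.

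The text then gives a general 12-week rule: "In case toxicity does not resolve to Grade 0-1 within 12 weeks after last infusion, trial treatment should be discontinued after consultation with the Sponsor". An exception follows at once. With the agreement of both Investigator and Sponsor, "patients with a laboratory AE still at Grade 2 after 12 weeks may continue treatment in the trial only if asymptomatic and controlled".

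Table 8, in the same section, sets hold, restart and discontinuation criteria by type of toxicity.

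- It has no haematological row. Such events fall to the All Other Drug-Related Toxicity row, which holds at grade 3 or severe and permanently discontinues at grade 4.
- In the AST, ALT or bilirubin row at grade 2, the discontinuation criterion is "Toxicity does not resolve within 12 weeks of last dose". The grade 2 row for renal failure or nephritis has the same criterion, plus a corticosteroid-reduction limit.
- Footnote 2, attached to the catch-all row, reads: "Permanently discontinue study drug for persistent Grade 2 adverse reactions for which treatment with study drug has been held", for reactions "that do not recover to Grade 0-1 within 12 weeks of the last dose".

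Two other places touch the subject. The note to Table 10 (section 7.5) says that for an irAE not down to grade 1 within 12 weeks "study therapy discontinuation should be considered after discussion with a Merck Clinical Director". Appendix 5, in its Haematologic block at grades 2 and 3, says "Withhold pembrolizumab, may restart if Grade 1 or resolved within 12 weeks".

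**The concern.** These are operative instructions for the same drug, in one section, for drug-related toxicity in general. An investigator working from the text and one working from the table can reach different actions for the same event, and nothing says which part prevails.

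Whether a patient is held, stopped for good or continued is a safety matter first. It also feeds the analysis. Section 9.1 reports dose administration, modifications, delays and duration of therapy. Section 3.2.2 closes the late-toxicity window 28 days after the last pembrolizumab dose, so the stopping rule in use also sets how long late toxicity is counted for that patient.

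**Working it through.** No sample size, power or event figure is at issue, so the check sets the rules side by side.

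| Situation | Text of 7.2.9.2 | Table 8 |
|---|---|---|
| Haematological, grade 3 | Not named in the haematological clause | Hold (catch-all row) |
| Haematological, grade 4 | Withhold | Permanently discontinue (catch-all row) |
| AST, ALT or bilirubin, grade 2, unresolved at 12 weeks | May continue if asymptomatic and controlled and Investigator and Sponsor agree | Discontinuation criterion met |
| Renal failure or nephritis, grade 2 on laboratory values, unresolved at 12 weeks | Same conditional continuation | Discontinuation criterion met |
| Other laboratory AE, grade 2, drug held, not recovered at 12 weeks | Same conditional continuation | Permanently discontinue (footnote 2) |

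**Haematological toxicity.** The lowest grade with a stated hold is 4 in the text and 3 in the table, a difference of 4 − 3 = 1 grade. At grade 4 the actions differ in kind: a hold, which allows a restart, against a permanent stop. The general note under Table 8, which stops treatment permanently for any life-threatening event, points the same way as the catch-all row.

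**Persistent grade 2 laboratory AE.** Both sources count 12 weeks from the last infusion or dose and both use recovery to grade 0-1, so timing does not explain the difference. The source of the table's rule depends on the laboratory value. For AST, ALT and bilirubin it is their own row. For renal events it is the renal row; creatinine is not named in Table 8. Footnote 2 applies only to toxicities in the catch-all row for which drug was held. The word permanently appears in footnote 2 but not in the liver and renal grade 2 cells, which only list non-resolution as the criterion for discontinuation.

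**Scale in the summaries.** With 18 patients, one patient handled differently is 1/18 = 5.6 percentage points of any discontinuation or dose-modification rate. This is the weight of one patient, not an estimate of effect. The protocol gives no frequency for persistent grade 2 laboratory AEs. The cited 25-patient pembrolizumab cohort (section 2.2.6.2) had one ALT rise and one thrombocytopenia at grade 3 or above. The ALT case falls in the grade 3-4 liver row, so it does not bear on the grade 2 rule. A single thrombocytopenia shows that the haematological conflict can arise but gives no usable rate.

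**What is untouched.** Section 4.2.1 defines DLTs by type, grade, duration and relatedness, plus interruption of radiotherapy. None of its criteria depends on whether pembrolizumab was held or stopped. The 3+3 rule and the cohort sizes in section 9.2 do not depend on it either.

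**The case against.** The best defence is that the text states a general rule and then a narrow exception, while Table 8, which calls itself a set of guidelines, simply tabulates the general rule. Continuation needs the Sponsor's agreement, and the opening sentence itself refers to Table 8 for severe or life-threatening events.

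Part of this stands. A reader might infer that a safety limit can be bypassed, or that sites would freely treat identical patients differently. For the laboratory AE the documents do not support that, because nobody continues without the one Sponsor agreeing. What remains is that Table 8 neither repeats the exception nor points to it, although it does flag a different exception in the grade 3-4 liver row. An investigator using the table alone would stop and would not know to ask.

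The defence is weaker for haematological toxicity. If the reference to severe events in Table 8 already brings in grade 3, the grade 4 threshold at the start of the sentence has no function. A hold and a permanent stop at grade 4 still cannot both apply.

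A reader might also infer three competing hold grades (4, 3 and 2), taking the grade 2 hold from Appendix 5. That goes too far. Section 7.2.9.2 sends events of clinical interest to Appendix 5, which covers immune-related events, and a lower threshold for those does not contradict a general rule. Table 12 does list any grade 4 anaemia whatever its mechanism, so the scopes overlap, but at grade 4 Appendix 5 and Table 8 both discontinue. The overlap gives no grade 2 conflict.

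Likewise, a reader might take the Table 10 note as a third outcome for the persistent grade 2 laboratory AE. Section 7.5 limits Table 10 to irAEs not detailed elsewhere, and liver and renal events are detailed elsewhere.

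**Conclusion.** The point holds as two conflicts between the text of section 7.2.9.2 and Table 8. For haematological toxicity the lowest hold grade differs by one, and grade 4 means a hold in one place and a permanent stop in the other. For a laboratory AE still at grade 2 after 12 weeks, the text allows conditional, Sponsor-agreed continuation, whereas the table calls for discontinuation without that exception.

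This rests on one reading of the table: that haematological toxicity belongs to the catch-all row because no other row covers it. Appendix 5 and Table 10 are not independent third rules, although their scope relative to Table 8 is left for the reader to work out.

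The consequence is for patient safety and for the dose-modification, exposure and discontinuation summaries, including the length of the late-toxicity window. How many patients would be affected cannot be estimated from the protocol. The primary endpoint definition and the sample size do not change. It should be corrected, but it does not call the design into question.

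**What to change.** Reconcile the text of section 7.2.9.2 with Table 8 and its footnotes so that each event has one hold-or-stop rule and one 12-week rule.

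- State in both places the same grade and action for haematological toxicity, preferably in a row of its own in Table 8.
- Either carry the laboratory exception into Table 8 by footnote, covering the liver, renal and catch-all rows, or remove it from the text.
- Add one sentence saying which passage prevails if they differ.
- Add one sentence on the scope of Table 10 and Appendix 5 relative to Table 8.

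The clinical team must decide which rule applies; this review takes no view. The cost is wording at the next protocol amendment. If patients have already been treated, record which rule was applied to any affected patient, so that the discontinuation and exposure tables can be read correctly.
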